The structures that CES is believed to affect are centrally located in the brain and are known to be involved in regulation of emotions. These subcortical brain structures are the reticular activating system, thalamus, and hypothalamus, and the limbic system. As the low intensity external charge supplied by CES reaches these deep brain structures there is a measurable physiologic result. Researchers from the University of North Texas used electroencephalogram (EEG) to show that CES is able to increase alpha brain waves (8–12 Hz) and decrease delta (0–3.5 Hz) and beta (12.5–30 Hz) brain waves. Increased alpha correlates with improved relaxation and increased mental alertness or clarity. Decreased delta waves indicate a reduction in fatigue. Beta-wave reductions between 20 and 30 Hz correlate with decreases in anxiety, ruminative thoughts, and obsessive/compulsive-like behaviors¹⁰.

While CES has been shown to be clinically effective in multiple studies, there are equal numbers of studies showing no effect or an indeterminate effect¹¹. In nearly all these studies the researchers call for further study with higher patient numbers and rigorous blinding. This study will be an extension of previous work showing potential efficacy in sleep, while introducing a new population in subacute stroke patients. We anticipate our findings will benefit future patients by providing an alternative to hypnotics which may have negative effects that are detrimental to the recovery of the stroke patient.

3. Concise Summary of Project

This will be a double blinded randomized clinical trial carried out at Zale-Lipshy and Parkland Hospital Inpatient Rehabilitation Facilities. Acute stroke patients with insomnia, identified by the Insomnia Severity Index (ISI), and who choose to participate in this study will be randomized to CES or sham CES. Patients who do not feel they are getting adequate sleep but want to continue in the study will be given the option to receive the standard of care medication as a rescue starting on the 3rd night.

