The study will begin on day 1 (d1) with the patient receiving 20 minutes of CES/sCES in the morning. This time will be distraction free without the entrance of laboratory technicians, nurses, housekeeping or other staff members. When this period is complete, they will participate in usual care. At midday they will be asked to complete the Karolinska Sleepiness Scale (KSS). The patient will wear the actigraph throughout the study. This procedure will be repeated for 7 treatment days. All procedures will be carried out by research team members or a trained nurse.

The intensity of the CES will begin on setting 2, standard setting recommended by the device manufacturer, and the patient will have the option to increase the intensity to setting 3 on the second treatment day if they feel they did not receive any benefit from the device.

If the patient does not feel they are getting adequate sleep the patient may choose to opt out of CES/sCES treatment and receive the standard of care medication for the remainder of the study. Patients who choose the SOC rescue will continue to be monitored with the actigraph. A patient may choose to leave the study at any time.

We will collect information on side effects for the CES treatment during the 7 days of the study.

Methods of assigning patients to treatment groups and blinding

Patients will be randomized to the active or sham treatment group using an online randomizer, Research randomizer (www.randomizer.org). A list of random numbers will be generated prior to the study. Patients will be assigned a random number in the order that the generator produces. All even patients will be assigned to the control group; odd numbered patients will be assigned to the treatment group.

Procedural responsibilities and oversight

Nursing staff at UTSW will be educated how to administer the CES and asked to help distribute and collect the Karolinska Sleepiness Scale questionnaire. Photos of proper placement and instructions will be posted in subjects' rooms for reference. Researchers affiliated with this project will apply and remove the actigraph watches and be responsible for data acquisition, cleaning and charging of the devices. Researchers affiliated with the study will be responsible for ensuring CES is delivered to the appropriate patients on the days required per protocol. Research personnel will be responsible for all study-related activities at Parkland.

5. Inclusion criteria

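### One odd/even list serves two hospitals that deliver the trial differently, and the analysis has no hospital term, so hospital mix by arm is left to chance; the cost is modest precision and clarity, not bias

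*Combined protocol and SAP*

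**What the plan says.** Section 3 has the trial "carried out at Zale-Lipshy and Parkland Hospital Inpatient Rehabilitation Facilities". Section 4, under the heading on procedural responsibilities, sets out who does what:

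- UTSW: "Nursing staff at UTSW will be educated how to administer the CES and asked to help distribute and collect the Karolinska Sleepiness Scale questionnaire".
- Parkland: "Research personnel will be responsible for all study-related activities at Parkland".
- Delivery of CES: "Researchers affiliated with the study will be responsible for ensuring CES is delivered to the appropriate patients on the days required per protocol".
- Actigraphs: "Researchers affiliated with this project will apply and remove the actigraph watches and be responsible for data acquisition, cleaning and charging of the devices".

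An earlier paragraph of Section 4 gives the general rule: "All procedures will be carried out by research team members or a trained nurse".

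On allocation, Section 4 says "A list of random numbers will be generated prior to the study". Numbers are taken in the order generated, and then "All even patients will be assigned to the control group; odd numbered patients will be assigned to the treatment group". It does not mention blocks, strata or separate lists by hospital.

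Section 14 plans a t-test for sleep time, a chi-square test for the KSS and a non-parametric test if the data are not normal. None of these includes hospital. No test is named for sleep efficiency, the subject of Specific Aim 2.

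**The concern.** Hospital is known before randomisation and goes with a documented difference in who applies the device and who helps with the KSS. It could also go with differences in ward conditions or case mix that affect sleep, although the documents report no such difference. A factor of this kind is usually balanced by design, adjusted for in the analysis, or both. Here neither is planned.

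At stake is the reading of one small trial. If one arm happens to hold noticeably more patients from one hospital, part of the observed difference in sleep may come from the hospital, and the planned test cannot separate the two. Hospital variation also stays in the error term, where it could be removed at almost no cost.

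**Working it through.** **Inputs from the documents.** 85 participants, two arms, two hospitals (opening section and Section 3); odd/even allocation from one list (Section 4); two-sided alpha .05 and 80% power (Section 14).

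**Assumed, because not stated.** The hospital split (68/17, 60/25, 59/26 and 43/42); a hospital difference in sleep of 60 min; a within-hospital SD of sleep time of 60–120 min.

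**The plan's own figure.** The sample size of 85 cannot be reproduced, since no target difference or SD is given. Solved backwards, d = (1.96 + 0.84) × √(2/42.5) ≈ 0.61 SD. This serves only as a yardstick.

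**Step 1: hospital mix with independent odd/even draws.** Let *a* of the *n1* patients at hospital 1 and *b* of the *n2* at hospital 2 be allocated to CES. These are independent Binomial(*n1*, ½) and Binomial(*n2*, ½). The imbalance is a/(a+b) − (n1−a)/(85−a−b). Exact enumeration gives:

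| Split (assumed) | SD of imbalance | At least 10 points | At least 20 points |
|---|---|---|---|
| 68/17 | 0.088 | 25.8% | 2.0% |
| 60/25 | 0.100 | 32.0% | 4.6% |
| 59/26 | 0.101 | 32.5% | 4.9% |
| 43/42 | 0.110 | 38.6% | 7.7% |

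**Step 2: overall arm sizes forced to 43/42.** With *a* hypergeometric, the chance of at least 10 points is 28% (68/17), 34% (60/25), 35% (59/26) and 39% (43/42). Equal arm sizes barely change the hospital imbalance.

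**Step 3: permuted blocks of 4 within hospital (illustrative size).** The largest possible imbalance is about 2 to 4 points, and the chance of at least 10 points is zero.

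**Step 4: effect on the estimate.** Shift = imbalance × hospital difference: 0.10 × 60 = 6 min and 0.20 × 60 = 12 min. With an SD of 60–120 min, the standard error of the arm difference is SD × √(1/43 + 1/42) = 13–26 min, so 6 min is about 0.2–0.5 standard errors. In SD units, a 20-point imbalance with a hospital effect of 0.25–0.5 SD shifts the difference by 0.05–0.10 SD, against the back-solved 0.61.

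**Step 5: precision lost without a hospital term.** At a near-even split, a hospital effect of δ SD multiplies the residual variance by 1 + 0.25δ². For δ = 0.5 this is 1.0625, so the standard error rises by about 3%. For δ = 1 (60 min on an SD of 60 min) it is 1.25, a rise of about 12%.

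**Step 6: type I error.** With a 0.5 SD hospital effect and simple randomisation, the unadjusted t-test rejects in 4.9% of 20,000 simulated null trials. With arms balanced within hospital but no hospital term, it rejects in 4.0%, slightly conservative. The hospital term should therefore accompany stratified lists.

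**Step 7: arm sizes.** With independent draws, arms differ by 11 or more with probability 0.278 and by 15 or more with probability 0.128. If 43/42 gives 80% power, 48/37 gives 79.3% and 50/35 gives about 78.8%.

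**The case against.** The strongest reply is that simple randomisation is valid in a small two-site trial, that chance imbalance is already allowed for in the test, and that a hospital term alone would recover most of the precision without making allocation more predictable. All of this stands, and it limits the weight of the point. It also supports the hospital term, which the plan lacks.

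A reader might draw three stronger conclusions that the documents do not support.

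- **Ward nurses run treatment and questionnaires at one hospital.** UTSW nurses administer CES but only help with the KSS. Researchers must ensure that CES is delivered as planned, and Section 4 gives actigraph handling and data acquisition to researchers without distinguishing hospitals. The outcomes of both Specific Aims come from the actigraph, so the operator difference bears mainly on device application and the KSS. That UTSW means only Zale Lipshy is inferred from the contrast with Parkland.
- **Arm sizes are uncontrolled.** The text does not say whether the list holds independent draws or a set of unique consecutive numbers. In the second case, odd/even gives about 43/42 once the list is used up, and the 28% and 13% figures fall away. Balance within hospital would remain uncontrolled (Step 2).
- **The result would be biased or the test invalid.** Allocation is random with respect to hospital, so expected bias is zero and the simulated error rate is not inflated.

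**Conclusion.** The point holds as a cheap improvement. Two hospitals with different delivery arrangements share one list with no described blocking or stratification, and the planned comparison ignores hospital. Across the assumed splits, a 10-point difference in hospital share has a chance of about 26–39% and a 20-point difference about 2–8%, whether or not overall arm sizes are equal.

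The consequence is some lost precision and a less clear single result. Its size rests on a hospital effect that the documents do not give: at an assumed 60 min, the shift is 6 to 12 min, and at a smaller effect it shrinks in proportion. If the hospitals do not differ in sleep, nothing is lost. Unequal arm sizes are a side issue: they depend on how the list is made and would cost about one percentage point of power.

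**What to change.** In Section 4, state how the numbers are generated. Replace the single odd/even list with one pre-made list per hospital, allocated 1:1 in permuted blocks of randomly varying size (for example 4 and 6) that is not disclosed to the wards.

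In Section 14, replace the unadjusted t-test with a linear model with treatment and hospital as factors, and name it for both sleep time and sleep efficiency. If the data are clearly non-normal, use a hospital-stratified rank test.

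If randomisation has already begun, leave the allocation alone and add the hospital term only, before the data are unblinded.

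The cost is a second list, one model term and one degree of freedom, with no extra patients or staff. Blocks are slightly more predictable than simple randomisation, which matters a little where ward nurses help deliver treatment; varying, undisclosed block sizes keep this small.
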